6.3 SUBGROUP ANALYSES IN GENERAL

All outcomes will be analysed with respect to the following subgroups:

- a) per primary diagnosis (in RCT1 anxiety vs. depression; in RCT2 per distress, adjustment disorder, and burnout);
- b) per employment status group at baseline (vacant vs. employed);

⁵ https://www.ema.europa.eu/en/documents/scientific-guideline/guideline-adjustment-baseline-covariates-clinical-trials_en.pdf

c) per IBBIS Team (two teams, Team North and Team Byen)

Furthermore,

d) divided in two groups by relative time of randomization: first and last temporal half of randomized participants.

Finally,

e) we will test for interaction between diagnostic group and treatment allocation group/arm.

No outcomes have other subgroup analyses planned.

6.4 OUTCOME DEFINITIONS

The outcomes are reported as in the study design articles (except for selected outcomes, see alterations to SAP version 1 in appendix). The numbers 1 through 64 denotes the outcome numbers for reference purposes for this SAP section.

| PRIMARY AND SECONDARY OUTCOMES and outcome numbering | | | | | | |
|---|--------------------|--|--|--------------------------|---------------------------|---------------------------|
| Outcome class | Data source | Outcome | | 6-month follow-up | 12-month follow-up | 24-month follow-up |
| Primary | DREAM database | Time from baseline to RTW | | | 1 | |
| Secondary | DREAM database | Proportion in ordinary work | | | 2 | |
| | DREAM database | Time from baseline to RTW | | 3 | | 8 |
| | Questionnaire | Depressive symptoms measured by Beck Depression Inventory (BDI) ⁸ | | 4 | | |
| | Questionnaire | Anxiety symptoms measured by Beck Anxiety Inventory (BAI) ⁹ | | 5 | | |
| | Questionnaire | Stress symptoms measured by Cohen perceived stress scale (PSS) ¹⁰ | | 6 | | |
| | Questionnaire | Social and work related function measured by WSAS ¹¹ | | 7 | | |

| PREDEFINED EXPLORATORY OUTCOMES and outcome numbering | | | | | | |
|---|--------------------|--|---|-----------------|-----------------|----|
| Outcome class | Data source | Outcome | Follow-up | | | |
| | | | 6-month | 12-month | 24-month | |
| Pre-defined exploratory outcomes | DREAM database | Weeks in stable work (≥ 4 weeks) from baseline to current follow-up | | 9 | 10 | |
| | | Weeks in stable work (≥ 8 weeks) from baseline to current follow-up | | | 11 | |
| | | Weeks in stable work (≥ 12 weeks) from baseline to current follow-up | | | 12 | |
| | | Weeks in work from baseline to follow-up | | | 13 | |
| | | Proportion in ordinary work | | | 14 | |
| | | Number of recurrent sick leaves | | | 15 | |
| | Questionnaires | | Symptoms of Distress, anxiety, depression and somatization by Four-Dimensional Symptom Questionnaire (4DSQ) ¹² | 16 | 17 | 18 |
| | | | Depressive symptoms measured by Beck Depression Inventory (BDI) ⁹ | | 19 | 20 |
| | | | Anxiety symptoms measured by Beck Anxiety Inventory (BAI) ⁹ | | 21 | 22 |
| | | | Stress-symptoms measured by Cohen perceived stress scale (PSS) ¹⁰ | | 23 | 24 |
| | | | Social and work related function measured by WSAS ¹¹ | | 25 | 26 |
| | | | Burn-out symptoms measured by Karolinska Exhaustion Scale (KES) ¹³ | 27 | 28 | 29 |
| | | | Health-related quality of life measured by EQ-5D-5L ¹⁴ | 30 | 31 | 32 |
| | | | General Quality of life scale measured by Flanagan's' QOLS ¹⁵ | 33 | 34 | 35 |
| | | | Self-efficacy concerning symptoms measured by IPQ subscale on personal control ¹⁶ | 36 | 37 | 38 |
| Return to work self-efficacy measured by RTW-SE ¹⁷ | 39 | 40 | 41 | | | |

| | | | | |
|--|---|----|----|----|
| | General self-efficacy measured by General Self-efficacy scale (GSS) ¹⁸ | 42 | 43 | 44 |
| | Client satisfaction with treatment measure measured by CSQ-8 ¹⁹ | 45 | | |
| | Presenteeism measured by Stanford Presenteeism Scale (SPS) ²⁰ | 46 | 47 | 48 |

HARM MEASURES and outcome numbering

| Outcome class | Data source | Outcome | Follow-up | | |
|---------------|-------------|--|-----------|----------|----------|
| | | | 6-month | 12-month | 24-month |
| Harm measures | LPR | Admission to somatic hospital-based (in-patient) health care at least once | | 49 | 50 |
| | LPR | Contact with hospital-based out-patient mental health care, at least once | | 51 | 52 |
| | | Admission to hospital-based in-patient mental health care, at least once | | 53 | 54 |
| | | Contact with emergency mental health care, at least once | | 55 | 56 |
| | LPR | Probable self-harm, at least once | | 57 | 58 |
| | LPR | Suicide | | 61 | 62 |
| | LPR | Death | | 63 | 64 |

6.5 HYPOTHESES AND NULL-HYPOTHESES

Stated below are the generic versions of all three hypotheses (H_1) and all three null-hypotheses (H_0) that apply to each outcome.

Regarding what is a “better outcome” is listed in section 6.6, defined for each outcome measure, respectively.

6.5.1 HYPOTHESES

This superiority trial hypothesizes that, for all outcomes,

H_{1A} Group 3, “Integrated IBBIS mental health care treatment and vocational rehabilitation”
conveys better outcomes than
Group 2, “IBBIS mental health care (and standard VR)”, and

H_{1B} Group 2, “IBBIS mental health care (and standard VR)”, and
conveys better outcomes than
Group 1, “Control group, treatment as usual (standard MHC and standard VR)”
and followingly

H_{1C} Group 3, “Integrated IBBIS mental health care treatment and vocational rehabilitation”
conveys better outcomes than
Group 1, “Control group, treatment as usual (standard MHC and standard VR)”
and followingly

Group 3 conveys better outcomes than Group 1,

since if

Group 3 outcome > Group 2 outcome > Group 1 outcome

then

Group 3 outcome > Group 1 outcome.

The groups are thoroughly described in the IBBIS Protocol and the SDAs.

6.5.2 NULL-HYPOTHESES

The corresponding null-hypotheses are

H_{oA} Group 3, “Integrated IBBIS mental health care treatment and vocational rehabilitation”
does not convey better outcomes than

Group 2, “IBBIS mental health care (and standard VR)”, and

H_{oB} Group 2, “IBBIS mental health care (and standard VR)”,

does not convey better outcomes than

Group 1, “Control group, treatment as usual (standard MHC and standard VR)”.

and followingly

H_{oC} Group 3 *does not* convey better outcomes than Group 1.

6.6 OUTCOME BENEFIT DIRECTION

Referring to the hypothesis section, this table describes whether a “better outcome” is a higher or lower score on the numeric outcome variables.

| Outcome | Is “better outcome” defined by lower or higher numbers? | |
|---|---|----------------------|
| Time from baseline to RTW | Lower | |
| Proportion in stable work | | Higher |
| Time from baseline to RTW | Lower | |
| Weeks in work (all variations of stability definitions) | | Higher |
| Number of recurrent sick leaves | Lower ⁶ | |
| Depressive symptoms measured by Beck Depression Inventory (BDI) ⁸ | Lower | |
| Anxiety symptoms measured by Beck Anxiety Inventory (BAI) ⁹ | Lower | |
| Stress symptoms measured by Cohen perceived stress scale (PSS) ¹⁰ | Lower | |
| Social and work related function measured by WSAS ¹¹ | Lower | |
| Symptoms of Distress, anxiety, depression and somatization by Four-Dimensional Symptom Questionnaire (4DSQ) ¹² | Lower | |
| Burn-out symptoms measured by Karolinska Exhaustion Scale (KES) ¹³ | Lower | |
| Health-related quality of life measured by EQ-5D-5L ¹⁴ | | Higher ²¹ |
| General Quality of life scale measured by Flanagan's' QOLS ¹⁵ | | Higher |
| Self-efficacy concerning symptoms measured by IPQ subscale on personal control ¹⁶ | | Higher ²² |
| Return to work self-efficacy measured by RTW-SE ¹⁷ | | Higher |
| General self-efficacy measured by General Self-efficacy scale (GSS) ¹⁸ | | Higher |
| Client satisfaction with treatment measure measured by CSQ-8 ¹⁹ | | Higher |
| Presenteeism measured by Stanford Presenteeism Scale (SPS) ²⁰ | | Higher ²³ |

⁶ A low number of recurrent sick leave is a positive outcome only if duration of index sick leave is ideally balanced between compared groups.

6.7 MISSING DATA IN GENERAL

In general, proportion of missing data will be reported per intervention group for all outcomes.

6.7.1 HANDLING OF MISSING DATA IN REGISTERS

For RTW-outcomes (outcomes based on the DREAM register) we expected *no missing data*, due to the nature of the Dream Register, prior to study inception. Missing data should only be in case of a participant moving out of Denmark. We considered these events to be so rare in our data that we would handle such missing data as *missing completely at random*. Thus, no imputation or other correction was considered necessary. We will report proportion of data missing.

We will report number of censored participants per treatment group.

At the of this updated version 2a of the SAP, we have realized that some data were missing due to DREAM database errors, against expectation. We included the cases with missing data in sensitivity analyses to explore the potential impact of the missingness.

6.7.2 HANDLING OF MISSING DATA IN QUESTIONNAIRE BASED, SELF-REPORTED DATA OUTCOME

For questionnaire-based outcomes, missing data will be handled as *missing at random*. To handle this, 100 multiple imputations will be performed, using following variables: stratification variables: diagnosis, municipality, employment status; age; gender; time to stable RTW; psychometric variables at baseline and all follow-up at outcome time: BDI, BAI, WSAS and PSS.

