1.2 SAP VERSION

This is the second version of the SAP.

¹ <https://clinicaltrials.gov/ct2/show/NCT02872051>

² <https://clinicaltrials.gov/ct2/show/NCT02885519>

Differences between version 1 and 2 are explicitly stated through a .docx-version of this newest version, where all changes are tracked, using the *Track changes* function in Microsoft Office Word. This file will be readily mailed through the corresponding author.

In brief, main changes revolves around the 24-month explorative outcomes: after analyses of 6- and 12-month outcomes we realized that results across work outcomes were heterogenous to a higher extent than expected. E.g., while the SAU group tended to have fastest RTW at 6-month follow-up, from explorative proportion over time-curves we realized that they might also tend to have a higher degree of recurrent sick-leave. Despite this, the SAU and INT groups still showed approx. the same number of weeks in work (when stability is disregarded) at 12-month follow-up. Followingly we speculate that the SAU group experiences faster RTW, but more recurrent sick leave. Therefore, we suggest that number of weeks in stable work is a better outcome, since this number is only high if RTW happens early, and if it is stable, and not disrupted by sick leave recurrence. We do though not know what stability threshold we should apply, and to *explore* this, we defined, prior to 24-month analyses, three different outcomes, with three different thresholds, see section 6.4. We plan these as sensitivity analyses.

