3.5 TIMING OF FINAL ANALYSIS

The researchers who will perform the 6- and 12-month outcome analyses (AH and JF) will be blinded from intervention group allocation, until the primary outcome and all 12-month follow-up outcome main analyses are completed. The true randomization group allocation is concealed, with values X, Y and Z reflecting group allocation in the blinded dataset. The randomization allocation variable conversion formula is until unblinding only known and hidden by an administrative co-worker, who will not perform or assist any analysis.

At the time of publication of SAP version 1, baseline distributional analyses, and unadjusted estimated marginal means-analyses of self-reported numerical secondary outcomes at 6-month follow-up (and only these) have been calculated *blinded*, but will not be published, since this was not complying with the SDAs, nor any SAP version.

All 24-month follow-up analyses will be conducted unblinded.

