6.8.2.7 REPORTING AND STATISTICAL METHODS TO HANDLE MISSING DATA

Same as 6.8.1.7.

6.8.3 ALL SELF-REPORTED, NUMERICAL OUTCOMES, AT 6-, 12-, AND 24-MONTH FOLLOW-UP AT (SECONDARY OUTCOMES ##4-7 AND PREDEFINED EXPLORATORY OUTCOMES ##16-48)

6.8.3.1 CALCULATION OF THE OUTCOME: SPECIFIC MEASUREMENT AND UNITS (AND TRANSFORMATION, WHERE APPLICABLE)

All outcomes are calculated as the sum of scores on the respective measurement scales.

All 6-month follow-up outcome analyses are calculating using baseline and 6-month follow-up observations.

All 12-month follow-up outcome analyses are calculating using baseline and 6- and 12-month follow-up observations.

All 24-month follow-up outcome analyses are calculating using baseline and 6-, 12-, and 24-month follow-up observations.

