6.8.3.2 SPECIFIC ANALYSIS METHOD AND RESULT PRESENTATION

Linear mixed-effects model with unstructured covariance. Results will be presented in pairwise group differences between outcomes, from the estimated marginal means from the model, and the confidence intervals of these differences.

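### Randomised arm is missing from the imputation list for the questionnaire outcomes, so the arm differences those analyses estimate are generally pulled toward zero

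*SAP*

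**What the plan says.** SAP section 6.7.2 treats missing questionnaire data as missing at random and specifies that "100 multiple imputations will be performed, using following variables: stratification variables: diagnosis, municipality, employment status; age; gender; time to stable RTW", and then "psychometric variables at baseline and all follow-up at outcome time: BDI, BAI, WSAS and PSS". Section 6.8.3.7 repeats the list. Neither place names randomised arm or says that imputation is run within arm, and nothing elsewhere in the SAP adds it.

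The analysis (section 6.8.3.2) is a linear mixed model with unstructured covariance: "Results will be presented in pairwise group differences between outcomes, from the estimated marginal means from the model". Sections 6.1 and 6.8.3.3 adjust it for the stratification variables. Section 6.8.3.1 sets which visits are used: "All 6-month follow-up outcome analyses are calculating using baseline and 6-month follow-up observations", with earlier visits added for the 12- and 24-month analyses.

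Register outcomes are handled differently. For them, section 6.7.1 says "no imputation or other correction was considered necessary".

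**The concern.** An imputation model should contain every variable in the analysis model, above all the one that defines the estimand. If arm is left out, each missing score is drawn from a distribution common to all arms given the listed predictors. The imputed part of the data then shows little or no arm difference, and averaging it with the observed part shrinks the estimated difference. This happens even when the plan's missing-at-random assumption is true.

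The list is hard to read as auxiliary variables added to an implied analysis model, because it spells out the stratification variables, which are already in that model.

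At stake are the four questionnaire secondary outcomes (4–7) and all exploratory questionnaire outcomes (16–48). In a superiority trial, diluted differences can turn real effects into null results.

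**Working it through.** **Outcomes affected (section 6.4).** Numbers 4–7 give 4 outcomes and 16–48 give 33, so 37 in all. BDI, BAI, PSS and WSAS at three visits make 12. For the other 37 − 12 = 25, the list does not name the scale being imputed. By visit there are 13 outcomes at 6 months (including 4–7), 12 at 12 months and 12 at 24 months.

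**Plan's own figures.** The SAP states no missing rate and no dilution figure. The inputs borrowed from it are 198 per arm, α = 0.05/3 = 0.0167 and 210 days to return to work in controls. The 198 reproduces. Two-sided Schoenfeld events are (2.394 + 1.282)² / (0.25 × (ln 1.5)²) ≈ 329. With exponential medians of 210 and 315 days, 730 days' accrual and 365 days' further follow-up, the event probabilities are about 0.887 and 0.777, and 329 / 1.664 = 197.7. The 0.8-power figure gives 153.3 against the stated 153.

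**Closed form.** Let m be the missing fraction, equal in all arms, and let the predictors carry no arm effect. Imputed values then average to the pooled mean in every arm:

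[(1 − m)μ₁ + m·μ_pool] − [(1 − m)μ₂ + m·μ_pool] = (1 − m)(μ₁ − μ₂)

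At m = 0.3, a true difference of 0.4 SD becomes 0.7 × 0.4 = 0.28 SD.

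**Simulation.** All of the following are assumptions except 198, 210 days and α:
- three arms of 198 with effects 0, −0.2 and −0.4 SD; the contrast is group 3 vs group 1;
- baseline correlation 0.5; missingness depends on baseline;
- exponential return-to-work time, correlated 0.4 with symptoms, cut at 182 or 365 days;
- proper regression imputation, 20 imputations, Rubin's rules, 600 replicates per cell;
- a baseline-adjusted regression in place of the mixed model.

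Share of the true effect recovered with arm omitted:

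| Situation | 10% missing | 20% | 30% | 40% |
|---|---|---|---|---|
| (a) Whole 6-month questionnaire missing, no arm effect on return to work | 0.89 | 0.80 | 0.71 | 0.60 |
| (b) As (a), hazard ratio 1.5 in the helpful direction | 0.91 | 0.84 | 0.75 | 0.69 |
| (c) 12-month score missing, 6-month score observed (correlation 0.65), no return-to-work effect | 0.95 | 0.90 | 0.86 | 0.80 |
| (c) with hazard ratio 1.5 | 0.96 | 0.94 | 0.91 | 0.87 |

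(d) If one 6-month scale is missing and another is observed (correlation 0.5 to 0.7), recovery at 30% missing is 0.81 to 0.89. With arm included, recovery is 0.98 to 1.02 throughout.

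**Power at 30% missing, arm omitted vs included.** (a) 70% vs 93%; (b) 81% vs 93%; (c) without a return-to-work effect, 92% vs 95%.

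**Opposing effects.** A separate simulation with missingness completely at random gave 0.89/0.81/0.72/0.59 when no predictor carried the effect, matching 1 − m. When the arm effect on return to work ran against the effect on symptoms, it gave 0.88/0.76/0.64/0.54, somewhat worse than 1 − m.

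**Null cases (30% and 40% missing, 1,500 replicates).** With no effect on anything, rejection is about 0.1–0.3% against a nominal 1.67%. With hazard ratio 1.5 and no symptom effect, the bias is about 0.02–0.03 SD away from zero and rejection stays at a few tenths of a percent at most.

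**The case against.** The best reply is that the list may not be the whole model. For 25 outcomes it omits even the scale being imputed, which must be present, so arm might be unstated for the same reason. This stands in part: the SAP does not show what was actually run. But a list that names the stratification covariates and leaves out arm directs an analyst to omit arm.

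Second, the phrase "psychometric variables at baseline and all follow-up at outcome time: BDI, BAI, WSAS and PSS" is loose and could admit other visits, and section 6.8.3.1 governs the analysis rather than the imputation. If later scores were used at 6 months, the losses would be closer to case (c) than to case (a). That is fair; the dilution becomes smaller but does not disappear.

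Third, the missing fraction is not a strict ceiling. Section 1.2 reports that the usual-care group tended to return to work fastest at 6 months, so opposing effects are conceivable and the relief in (b) may be optimistic. This also stands, and it makes the problem slightly worse.

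Three other defences fail:
- Blinding is no obstacle, because the analysts' dataset had arm coded, "with values X, Y and Z reflecting group allocation in the blinded dataset", and the 24-month analyses are unblinded.
- A mixed model on the observed data alone would be sound under missing at random, but the SAP says missing data are handled by imputation.
- The sensitivity analysis in section 6.2.1 fills gaps with the mean ± 2 SD and states no arm-specific value. With equal missingness, a common fill-in value also shrinks differences by 1 − m.

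**Conclusion.** The concern holds: the imputation rule is wrong as written. True differences on outcomes 4–7 and 16–48 are generally underestimated, by up to about the missing fraction when the listed predictors carry no arm effect, less when observed scores or return-to-work time carry it, and slightly more when the return-to-work effect opposes the symptom effect. Exposure is greatest for the 13 six-month outcomes if whole questionnaires are missing together and only baseline and 6-month data are used.

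The direction follows from algebra. The sizes rest on assumed missing rates, a 0.4 SD effect and assumed correlations. The error mainly risks missing real effects rather than creating false ones. The primary outcome (1) and the register-based secondary outcomes (2, 3 and 8) are not imputed and are unaffected. This should be fixed, but it does not threaten the trial's main result.

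**What to change.** In sections 6.7.2 and 6.8.3.7, add randomised arm to the imputation model or state that imputation is done separately by arm; the X/Y/Z code is enough. Also add each analysed scale at every visit where it is scheduled. The item listed as "Client satisfaction with treatment measure measured by CSQ-8" is scheduled at 6 months only, so it has no other visit to add.

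For the 24-month analyses this is a wording change in two sections and needs no new data. Section 1.2 shows that version 2 was written "after analyses of 6- and 12-month outcomes", so the SAP should also state whether arm was in the imputation model for those. If it was, a clarifying sentence suffices. If not, re-run the 6- and 12-month questionnaire analyses with arm included and report the re-run as a post-hoc correction beside the result already obtained. The cost is computing time and open disclosure of the change.

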6.8.1 TIME TO RETURN TO WORK-OUTCOMES (OUTCOMES #1, #3 AND #8)

This section describes primary outcome *Time from baseline to RTW* at 12-month follow-up (1), and the secondary outcomes *Time from baseline to RTW* at 6- (outcome 3) and 24-month follow-up (outcome 8). The 24-month follow-up outcome will be calculated no earlier than June 2020. The other two, readily after the publication of this SAP, but before unblinding of analysts.

6.8.1.1 CALCULATION OF THE OUTCOME: SPECIFIC MEASUREMENT AND UNITS (AND TRANSFORMATION, WHERE APPLICABLE)

Time from baseline to RTW is defined as the number of weeks from randomization date, to stable return to work. Stable return to work is defined as 4 weeks consecutively in work, i.e. with no sick leave benefit those 4 weeks in the Dream register, and a so-called “branch code” in at least some of this 4 week period (benefit codes are week-based, branch codes are month based, and hence a period of 4 weeks may represent only one month, or overlap a two month period; in the latter case, return to work will be attained if at least one of these registrations contains a branch code; a branch code means that the individual received salary from an employer in this period). Time of event is first day of the four weeks.

These events will define censoring: 1) moving out of the country, 2) death, 3) public retirement pension (Da.: “Folkepension”), and 4) voluntary early retirement scheme (Danish: “Efterløn”).

At randomization all participants are, according to inclusion criteria, on sick-leave from employment or vacancy. Some participants might be on sick-leave from an employment in a *flexjob*⁷, and hence receiving *flexjob benefit* during employment. This benefit is changed to *flexjob sick-leave benefit* similar to regular sick leave benefit for participants not granted flexjob benefit prior to randomization. In these cases (of participants granted flexjob benefit prior to randomization) RTW is defined as either not receiving flexjob sick-leave benefit for four consecutive weeks, along with a registered branch code as above mentioned (or alternatively not receiving flexjob benefit, but an ordinary salary indicated by a branch code during those four weeks).

⁷ “Flexjob” is one of the Danish benefit schemes; it is a subsidy granted those with a chronic reduced work capacity

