6.8.1.7 REPORTING AND STATISTICAL METHODS TO HANDLE MISSING DATA

On RWT-outcomes we expect *no missing data*, due to the nature of the Dream Register. Missing data will only be in case of a participant dying or moving out of Denmark. We consider these events to be so rare in our data that we will handle such missing data as *missing completely at random*. Thus, no imputation or other correction is necessary. We will report proportion of data missing.

We will report number of censored participants per treatment group.

6.8.2 PROPORTION IN ORDINARY WORK AT 12-MONTH FOLLOW-UP (SECONDARY OUTCOME) AND 24-MONTH FOLLOW-UP (EXPLORATORY OUTCOME) (OUTCOME #2 AND #14)

6.8.2.1 CALCULATION OF THE OUTCOME: SPECIFIC MEASUREMENT AND UNITS (AND TRANSFORMATION, WHERE APPLICABLE)

This outcome is calculated as the share of the treatment allocation group that on the time of follow-up was in stable RTW (≥ 4 weeks). Stable RTW if defined exactly as in the primary outcome, see 6.8.1.1.

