6.8.3.7 REPORTING AND STATISTICAL METHODS TO HANDLE MISSING DATA

Proportion and amount of missing data per outcome variable per follow-up event per treatment group will be reported.

To handle missing data, 100 multiple imputations will be performed, using following variables: stratification variables: diagnosis, municipality, employment status; age; gender; time to stable RTW; psychometric variables at baseline and all follow-up at outcome time: BDI, BAI, WSAS and PSS.

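### The imputation list for the questionnaire scales enters time to stable return to work with no return indicator, so it carries work status poorly and can modestly dilute arm differences

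*SAP*

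**What the plan says.** SAP 6.7.2 treats missing questionnaire data as missing at random and states: "100 multiple imputations will be performed, using following variables: stratification variables: diagnosis, municipality, employment status; age; gender; time to stable RTW". After the stratification variables the list reads "age; gender; time to stable RTW; psychometric variables at baseline and all follow-up at outcome time", followed by the four scales BDI, BAI, WSAS and PSS, and 6.8.3.7 repeats it. Neither section names a return indicator, a value for participants who have not returned, a time horizon for the RTW variable, or allocation arm.

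Section 6.8.1.1 defines the variable: "Time from baseline to RTW is defined as the number of weeks from randomization date, to stable return to work". It also lists censoring events ("These events will define censoring: 1) moving out of the country, 2) death, 3) public retirement pension" and early retirement). Section 6.8.1.2 analyses this time by Cox regression, and 6.8.1.7 adds: "We will report number of censored participants per treatment group". So the plan treats it as a censored time when it is an outcome, but does not say how the censoring is handled when it is an imputation variable.

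The scales are analysed under 6.8.3.2 ("Linear mixed-effects model with unstructured covariance") and reported as pairwise arm differences.

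**The concern.** A participant who has not returned has no time to stable RTW. An analyst following the list has two obvious options. One is to set the time to the end of follow-up, so that a non-returner looks like someone who returned on the last day. The other is to leave it blank and impute it, so that non-returners receive times learned from returners. Both blur whether the person is back at work, which is probably one of the better predictors of symptom and function scores, and plausibly of who fails to answer. If arms differ in return to work, the imputed scores then carry too little of that difference. The two options also give different answers, and the plan does not choose between them.

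**Working it through.** **1. Reading of the 210 days (SAP 3.3).** The section calls 210 days a mean. Test which reading reproduces the stated 198 per group. Inputs: two-sided α = 0.05/3, power 0.9, ratio 1.5, accrual 730 days, follow-up 365 days.

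- (z₁₋α/₂ + z₁₋β)² / (ln 1.5)² = (2.394 + 1.282)² / 0.1644 ≈ 82.2.
- Event probability with uniform accrual: p = 1 − e^(−λF)(1 − e^(−λA))/(λA). A median of 210 days gives 0.887; a median of 315 days (210 × 1.5) gives 0.777.
- n = 82.2 × (1/0.887 + 1/0.777) ≈ 198, as stated.

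Read as a mean, the same formula gives 180, or 170 with the ratio applied the other way. The median reading is therefore used below.

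**2. Share without a return time** (exponential times, cut at each follow-up): S(t) = 0.5^(HR × t / median).

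| Planning value | 6 months, control / HR 1.5 | 12 months, control / HR 1.5 | 24 months, control / HR 1.5 |
|---|---|---|---|
| Median 210 days | 55% / 40% | 30% / 16% | 9% / 3% |
| Mean 210 days | 42% / 27% | 18% / 7% | 3% / 0.5% |
| Median 104 days (low end in 3.3) | 30% / 16% | 9% / 3% | 1% / 0.1% |

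Example: 0.5^(365/210) = 0.30.

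**3. Effect on arm differences, time capped.** Simulation with 198 per arm, two arms, 600 runs, 20 imputations, control median 30 weeks, HR 1.5, baseline SD 10 with slope 0.5, residual SD 8.5, and a baseline-adjusted linear model. Effects and missingness are assumptions, since the SAP gives none. Simulation standard errors are 0.03–0.05.

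| Direct arm effect; at-work effect; % missing non-returners/returners; month | Full data | As listed: time, no arm | Time + indicator, no arm | Time + arm | Time + indicator + arm |
|---|---|---|---|---|---|
| −4; −6; 40/40; 12 | −4.80 | −3.16 | −3.24 | −4.78 | −4.79 |
| −4; −6; 50/30; 12 | −4.80 | −3.32 | −3.48 | −4.74 | −4.83 |
| −4; 0; 40/40; 12 | −4.01 | −2.49 | −2.49 | −4.07 | −4.06 |
| 0; −10; 40/40; 12 | −1.30 | −1.21 | −1.31 | −1.31 | −1.31 |
| 0; −10; 50/30; 12 | −1.34 | −1.12 | −1.35 | −1.23 | −1.35 |
| −4; −6; 50/30; 6 | −4.82 | −3.13 | −3.24 | −4.74 | −4.78 |

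- With arm in the model, the worst capped case here loses (1.34 − 1.23)/1.34 ≈ 8%. The 6-month case loses (4.82 − 4.74)/4.82 ≈ 2%.
- As listed, the first row loses (4.80 − 3.16)/4.80 ≈ 34%. The indicator alone recovers (3.24 − 3.16)/(4.80 − 3.16) ≈ 5% of that; adding arm recovers nearly all.
- If the effect runs wholly through work status, the indicator alone repairs the loss (fourth and fifth rows).

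**4. Both codings.** Further simulations had arm in the imputation model, HR 1.5, an at-work effect of 0.5 (about half an SD) and more missing data in non-returners. If the whole effect runs through work status, the 12-month loss is about 14–24% capped and 20–37% blank-and-imputed. With a sizeable direct arm effect it is about 2–6%. At 6 months it is about 0–13%. The largest absolute loss is about 0.03 SD. With an indicator plus Nelson-Aalen hazard, the error is within about 5%.

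**The case against.** The case that this hardly matters is strong on size. With 198 per arm and complete data, the standard error of an unadjusted pairwise difference is √(2/198) ≈ 0.10 SD, so the 98.3% interval has half-width 2.394 × 0.10 ≈ 0.24 SD. A loss of 0.03 SD is about one eighth of that. The larger percentages need unequal missingness and an effect running mainly through work status. The 55% and 30% are control-arm shares at the slowest planning value, and assume that the time is cut at each follow-up, which the SAP does not say. Capping at least leaves non-returners as a separate mass at the cut-off. Few would lack a return time by 24 months. All of this stands, and it keeps the point minor.

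A reader might infer more than the document supports:

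- That the SAP enters the time as an ordinary complete variable. It gives only a bare list entry; the coding is unstated.
- That this entry is the main cause of diluted arm differences. Whenever there is a direct arm effect, the absence of arm from the list matters far more.
- That the 12-month losses fall on secondary outcomes. Section 6.4 places outcomes 4–7 at 6 months; the 12-month depression, anxiety, stress and function scales (19, 21, 23 and 25) are exploratory.
- That the censoring count in 6.8.1.7 bears on questionnaire imputation. It concerns reporting of the RTW outcomes only.

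None of this supplies the missing coding rule. The list is fixed in the SAP itself, and as written it leaves the analyst a choice that changes the estimates.

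**Conclusion.** The point holds as a minor one. The listed RTW time is unobserved for a material share at 6 and 12 months, and without a return indicator it carries work status poorly under either obvious coding. With arm in the imputation model, the dilution is roughly 0–13% at 6 months and 0–37% at 12 months, at most about 0.03 SD. It is largest when the effect runs wholly through work status and non-returners answer less often.

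These figures rest on assumed effects and missingness, exponential return times and HR 1.5. The table above comes from a single-scale linear model in place of the planned mixed model; observed values on the correlated scales would reduce the loss. The figures do not show that any reported conclusion on outcomes 4–7 would change.

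**What to change.** In 6.7.2 and 6.8.3.7, replace the time-to-stable-RTW entry with two variables derived from DREAM: stable return by the questionnaire date (yes/no), and the Nelson-Aalen cumulative hazard at the observed or censored time. Weeks in work to that date is an acceptable alternative to the hazard. In the same edit, add allocation arm to the imputation model, or impute within arm; the recoding alone is not enough if there is a direct arm effect.

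Use the revised model for the 24-month scales. For outcomes 4–7 and the 12-month scales, report a re-run as a labelled sensitivity analysis only: SAP 1.2 says that version 2 followed the 6- and 12-month analyses, so a new imputation model cannot replace those results.

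The cost is two derived variables, one added term or a split by arm, and some extra analysis and reporting.
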